7.4 Drug Information on Mitoxantrone

7.4.1 Mechanism of Action: Mitoxantrone (dihydroxyanthracenedione) is an anthracenedione derivative that intercalates with DNA, resulting in inhibition of nucleic acid synthesis.

7.4.2 Pharmacokinetics: Mitoxantrone is 78% bound to plasma proteins. A three-compartment model was described after a single intravenous dose of mitoxantrone. The mean alpha half-life is 6 to 12 minutes, the mean beta half-life is 1.1 to 3.1 hours, and the mean terminal (gamma) or elimination half-life is 23 to 215 hours (median 75 hours). Mitoxantrone has extensive distribution into body tissues and is metabolized in the liver to two main inactive metabolites (monocarboxylic acid derivative and dicarboxylic acid derivative). The major route of excretion for mitoxantrone appears to be biliary into the feces; approximately 11% of the dose is recovered in the urine within 5 days of drug administration, with 65% of this being unchanged drug.

7.4.3 Adverse Effects: *Common adverse effects (occurring in >10% of patients)* include edema, fever, fatigue, headache, alopecia, nausea/vomiting, diarrhea, mucositis/stomatitis, myelosuppression, weakness, dyspnea, cough, and infection. *Less common adverse effects (occurring in 1 to 10% of patients)* include congestive heart failure, decreased left ventricular ejection fraction (LVEF), hypertension, chills, anxiety, cutaneous mycosis, hypocalcemia, hypokalemia, hyponatremia, menorrhagia, jaundice, myalgia, arthralgia, renal failure, proteinuria, rhinitis, diaphoresis, and infection.

Mitoxantrone may cause cardiac toxicity with prolonged administration and doses exceeding 80 to 100 mg/m²; Appendix B provides an overview of the cardiotoxicity index of individual anthracyclines as well as mitoxantrone. When used after doxorubicin, cardiotoxicity is more frequent; an analysis by the Southwest Oncology Group revealed a risk of 6% at 134 mg/m² prior doxorubicin and 60 mg/m² mitoxantrone, rising to a 15% risk at 120 mg/m² mitoxantrone. Cardiac events reported included arrhythmias, decreased left ventricular function, chronic heart failure, tachycardia, ECG changes, and, infrequently, myocardial infarction. Bradycardia has been rarely reported. Patients with prior treatment with anthracyclines, prior mediastinal radiotherapy, or with preexisting cardiovascular disease may have more frequent occurrences of cardiac toxicity.

7.4.4 Reconstitution: Mitoxantrone must be diluted prior to use. The dose of mitoxantrone should be to at least 50 mL with either 0.9% Sodium Chloride Injection (USP) or 5% Dextrose Injection (USP). Mitoxantrone may be further diluted into Dextrose 5% in Water, Normal Saline or Dextrose 5% with Normal Saline and used immediately.

7.4.5 Administration and Compatibility: Care in the administration of mitoxantrone will reduce the chance of extravasation. Mitoxantrone should be administered into the tubing of a freely running intravenous infusion of 0.9% Sodium Chloride Injection, USP or 5% Dextrose Injection, USP. Care should be taken to avoid extravasation at the infusion site and to avoid contact of mitoxantrone with the skin, mucous membranes, or eyes. If any signs or symptoms of extravasation have occurred, including burning, pain, pruritis, erythema, swelling, blue discoloration,

or ulceration, the injection or infusion should be immediately terminated and restarted in another vein.

Mitoxantrone should not be mixed in the same infusion as heparin since a precipitate may form.

7.4.6 Storage and Stability: Mitoxantrone should be stored between 15°C - 25°C (59°F-77°F)

8.0 EVALUATION AND END POINT DEFINITIONS

8.1 Treatment Response and Outcome

Treatment response (e.g. morphologic/cytogenetic/molecular CR/CRi) or treatment failure (e.g. resistant disease, aplasia, morphological or molecular/cytogenetic relapse) as well as treatment outcome (e.g. overall survival, relapse-free survival, event-free survival, and remission duration) will be determined by peripheral blood count and bone marrow evaluation as per Section 6.5 and categorized according to criteria recommended by International Working Groups.^{17,18} Patients are routinely assessed for the presence of minimal residual disease (MRD) as detected by multi-parameter flow cytometry and cytogenetic assessment, as per institutional practice.

8.2 Monitoring of Exploratory Endpoints

8.2.1 Quality of life (QOL) assessment

In order to measure QOL, we will use the European Organization for Research and Treatment of Cancer Quality of Life Questionnaire (EORTC QLQ-C30), a validated 30-item instrument that includes 5 functional scales, 3 symptom scales, a global health scale, and 6 single items (APPENDIX C). Standardized scores for each scale range from 0 to 100 (higher scores representing better domain-specific QOL),¹⁹ with a minimally clinically important difference of 10 points.²⁰ We will request survey completion upon study enrollment as well as after each on-study treatment cycle. Given that patients do not always fill out questionnaires due to illness, time or other constraints, we will measure percentage of returned surveys as one of our feasibility outcomes.

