6.0 TREATMENT PLAN

This study is a single-center, open-label randomized pilot study of lower-dose vs higher-dose G-CLAM for medically less fit adults with newly diagnosed AML or analogous myeloid neoplasms at the Fred Hutchinson Cancer Research Center/University of Washington/Seattle Cancer Care Alliance.

Study Overview

In this pilot study, patients meeting the inclusion/exclusion criteria and their primary oncologists are asked whether or not they would agree to participate in the randomized treatment assignment (APPENDIX D). Patients agreeable to randomization will be assigned in a 1:1 ratio to the higher-dose G-CLAM arm or the lower-dose G-CLAM arm that utilizes lower doses of cladribine, cytarabine, and mitoxantrone. For those who wish to not be randomized, the reasons to decline randomization will be recorded, and patients will be allowed to receive the treatment intensity of their choosing. Patients will receive higher-dose or lower-dose G-CLAM as follows:

Treatment arm	G-CSF (SC, D0-D5)	Cladribine (IV 2h, D1-D5)	Cytarabine (IV, D1-D5)	Mitoxantrone (IV, D1-D3)
Higher-dose G-CLAM	300 or 480 µg*	5 mg/m ²	2,000 mg/m ² **	18 mg/m ²
Lower-dose G-CLAM	300 or 480 µg*	2 mg/m ²	100 mg/m ² ***	6 mg/m ²

*Dosing based on patient weight: <76kg vs. ≥76 kg; **over 2 hours; ***over 1 hour

After study enrollment, patients will receive a first cycle of G-CLAM on one of the designated treatment arms. Post-induction bone marrows will be reassessed upon blood count recovery or between day Days +28 to +35 after start of chemotherapy, whichever occurs first. If a response other than a measurable (“minimal”) residual disease-negative (MRDneg) CR is achieved, the patient will receive re-induction with G-CLAM at the same dosing. Patients who achieve a morphologic CR or CR with incomplete count recovery (CRi) with up to 2 courses of higher-dose G-CLAM or up to 6 courses of lower-dose G-CLAM can receive consolidation therapy with G-CLA (i.e. mitoxantrone omitted; up to 4 cycles with high-dose G-CLA and up to 12 cycles of low-dose G-CLA).

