6.5 Assessment for Response after First Induction Course

A bone marrow aspirate should be obtained upon blood count recovery (i.e. ANC >1,000/µL and platelet count >100,000/µL) or between Days +28 to +35 after start of G-CLAM chemotherapy, whichever occurs first; a bone marrow biopsy need only be obtained during this procedure if spicules are absent from the aspirate sample.

- 6.5.1 Patients achieving an MRDneg CR: Patients are eligible to receive consolidation therapy with G-CLA (dosing as per section 6.6): up to 4 cycles on the high-dose arm and up to 12 cycles on the low-dose arm
- 6.5.2 Patients achieving a MRDpos CR or CRI: Patients are eligible for a second cycle of induction therapy using the same dosing guidelines as cycle 1 or may proceed to consolidation therapy with G-CLA as per 6.6, per discretion of treating attending.
- 6.5.3 Patients with persistent disease: Patients with persistent disease ($\geq 5\%$ blasts) are eligible for a second course of induction chemotherapy at the same dosing used in cycle 1 provided all non-hematologic toxicities have resolved to Grade <2. If they are not in CR or CRI after the 2nd induction course, they will be removed from the study.
- 6.5.4 Patients with persistent aplasia without evidence of disease after Day +49: patients will be removed from protocol.

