6.6 Consolidation Therapy

After achievement of a CR/CRI (irrespective of MRD) with 1-2 courses of G-CLAM therapy, patients are eligible for post-remission therapy with G-CLA.

- 6.6.1 The treatment is identical to the induction course but without mitoxantrone (i.e. G-CSF, cladribine, and cytarabine, or “G-CLA” at same dose level as induction). If a patient had excessive toxicities (grade ≥ 3 non-hematologic toxicity excluding neutropenic fever and infections) during induction, a dose reduction can be considered as described in sections 6.8 and 6.9, as well as APPENDIX B.
- 6.6.2 Post-remission courses should start within 6 weeks of achieving CR/CRI once patients have recovered to \leq Grade 2 toxicities from the previous course of therapy.
- 6.6.3 Patients on the higher-dose arm can receive up to 4 courses of consolidation therapy.
- 6.6.4 Patients on the lower-dose arm can receive up to 12 cycles of consolidation therapy.
- 6.6.5 Patients can proceed to transplantation barring contraindications and if a suitable donor is available.

6.7 **Monitoring during/after Induction and Consolidation Therapy**

For patient monitoring, the following studies and study intervals are suggested and will be performed at the physician's discretion:

- 6.7.1 Complete blood counts with differential blood count, including immature cells/blast, and platelet count at least 2 times weekly until ANC >500/ μ L and then at least weekly until platelet count >100,000/ μ L.
- 6.7.2 Metabolic panel, including bilirubin, ALT/AST, and creatinine at least weekly until ANC >1,000/ μ L and platelet count >100,000/ μ L.
- 6.7.3 If patients develop signs or symptoms suggestive of cardiac dysfunction, LVEF should be assessed using the same method to evaluate baseline LVEF status (MUGA scan or echocardiography, or other appropriate diagnostic modality).

6.8 **Dose Modifications of Chemotherapeutic Drugs for Induction or Subsequent Treatment Cycles for Higher-Dose Arm**

For patients who have organ dysfunction at baseline—defined as a serum creatinine > 2.0 mg/dL or a bilirubin concentration is $\geq 3 \times$ IULN— or those who experienced \geq Grade 3 non-hematologic toxicities excluding neutropenic fever and infections during the first induction, a dose reduction can be considered as follows (see also APPENDIX B):

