10.0 SUBJECT DISCONTINUATION OF ACTIVE TREATMENT

10.1 Criteria for Removal from Treatment

All reasons for discontinuation of treatment must be documented:

10.1.1 Completion of protocol treatment.

10.1.2 Arrival to the transplant service for planned HCT.

- 10.1.3** Initiation of any leukemia-directed therapy other than protocol therapy
- 10.1.4** Failure to achieve a CR or CRi after 2 courses of therapy with higher-dose G-CLAM or 6 courses of therapy with lower-dose G-CLAM.
- 10.1.5** Persistent aplasia (ANC <500/ μ L or platelets <50,000/ μ L) without evidence of leukemia after Day +49.
- 10.1.6** Relapse after achievement of CR/CRi during treatment.
- 10.1.7** Adverse toxicities that prevent continuation with study treatment.
- 10.1.8** Withdrawal of consent; the patient may withdraw from the study at any time for any reason.

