14.3.2 Exploratory endpoints

This pilot study will use exploratory, descriptive, and observational methods to

- 1) Evaluate the attitude of patients and physicians toward randomization and explore reasons for treatment preference
- 2) Evaluate whether the ability to assess fitness for intensive chemotherapy can be improved by an augmented treatment-related mortality (TRM) score that includes additional (co-

morbidity) factors, and to compare the ability of physicians of the prediction algorithm(s) and physician to assess the likelihood of early death

3) Estimate differences between patients treated with lower-intensity G-CLAM and those treated with higher-intensity G-CLAM with regard to anti-leukemic efficacy (response, duration of response) and survival, QOL, and medical resource utilization as well as care cost

Importantly, this trial is not powered to detect statistically significant differences between the study arms for these clinically important endpoints. Rather, the primary goal is to estimate outcomes with both treatment intensities to inform a subsequent larger study, should follow-up investigation appear warranted.

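### QOL is surveyed only while patients are on treatment, so between-arm QOL differences after course 2 can partly reflect who is still being surveyed

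*Combined protocol and SAP*

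**What the plan says.** **Survey schedule.** Section 8.2.1: "We will request survey completion upon study enrollment as well as after each on-study treatment cycle". The important difference on the QLQ-C30 is put at 10 points. The only provision for missing surveys is to measure the percentage returned. Section 10.2 follows patients after treatment for event-free, relapse-free and overall survival, and lists no QOL.

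**When treatment, and with it the surveys, ends.**
- Section 10.1.4 ends treatment on: "Failure to achieve a CR or CRi after 2 courses of therapy with higher-dose G-CLAM or 6 courses of therapy with lower-dose G-CLAM".
- The Section 6.0 overview agrees, in that CR or CRi may be reached with "up to 2 courses of higher-dose G-CLAM or up to 6 courses of lower-dose G-CLAM can receive consolidation therapy".
- Section 6.5.3, on patients with persistent disease, names no arm: "If they are not in CR or CRI after the 2nd induction course, they will be removed from the study".
- Section 6.6 opens consolidation to patients who reach CR/CRi "with 1-2 courses of G-CLAM therapy", again with no arm named.
- Consolidation is "up to 4 cycles with high-dose G-CLA and up to 12 cycles of low-dose G-CLA" (Section 6.0); Section 6.6 gives the same caps.
- Arrival at the transplant service, other leukemia therapy, relapse and toxicity also end treatment (Section 10.1).

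**Intended use.** Objective 2.2.4 is to describe the effect of intensity on QOL. Section 14.3.2 goes further: "Estimate differences between patients treated with lower-intensity G-CLAM and those treated with higher-intensity G-CLAM", with QOL among the listed outcomes. It says the trial is not powered for these outcomes and that the estimates are meant to inform a larger study. It names no QOL time point, and no handling of death, exit or missing surveys.

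**The concern.** Whether a patient is surveyed late depends on events after treatment starts, above all on response, and the exit rule may differ by arm. If non-responders leave after 2 courses in one arm and may stay for 6 in the other, the two groups surveyed from course 3 are different kinds of patient. Aligning the surveys by calendar time cannot help, because a patient who has left treatment is never asked. Randomization does not protect a comparison that is restricted afterwards by an arm-specific rule.

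The percentage of surveys returned will not show the problem either. If requests are tied to on-study cycles, a removed patient adds nothing to the denominator.

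At stake is an exploratory estimate. It is nonetheless one of those the protocol wants to carry into the design of a larger trial of treatment intensity.

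**Working it through.** The plan gives no QOL sample size, power or expected difference, so there is no stated figure to reproduce except the 10-point threshold.

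**Step 1. Maximum survey occasions** (enrollment + induction courses + consolidation courses)

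| Reading | Higher-dose | Lower-dose |
|---|---|---|
| Sections 6.0 and 10.1.4 (2 vs 6) | 1 + 2 + 4 = 7 | 1 + 6 + 12 = 19 |
| Sections 6.5.3 and 6.6 (2 in both arms) | 1 + 2 + 4 = 7 | 1 + 2 + 12 = 15 |

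These are ceilings, not expected counts. They do not measure bias.

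**Step 2. Who can be surveyed from course 3 on**
- 2-versus-6 reading: higher-dose, only patients in CR/CRi. Lower-dose, patients in CR/CRi plus non-responders still in induction, up to course 6.
- 2-in-both reading: only patients in CR/CRi in each arm, then thinned by transplant, relapse, toxicity and caps of 4 versus 12.

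**Step 3. Size under the 2-versus-6 reading (illustration)**

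Suppose intensity has no effect on QOL once response status is known. Let r be the share of survivors in CR/CRi by course 2, c the share of lower-dose non-responders who continue, and g the QOL gap, responders minus non-responders. The non-responder share among lower-dose patients still surveyed at course 3 is

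s = c(1 − r) / [r + c(1 − r)],

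and the spurious difference, higher minus lower, is g × s.

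Assumptions, none given in the documents: r from 30% to 60%, equal in both arms; c from 50% to 100%; g from 5 to 20 points. For head counts I take 25 patients per arm (half of the 50 in Section 14.2) and 27% early death, the historical rate in Section 14.4: 25 × 0.73 = 18.25 survivors per arm.

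| r | c | Higher-dose n | Lower-dose n | s | g = 5 | g = 10 | g = 20 |
|---|---|---|---|---|---|---|---|
| 30% | 100% | 5.5 | 18.2 | 0.70 | 3.5 | 7.0 | 14.0 |
| 30% | 50% | 5.5 | 11.9 | 0.54 | 2.7 | 5.4 | 10.8 |
| 60% | 100% | 10.9 | 18.2 | 0.40 | 2.0 | 4.0 | 8.0 |
| 60% | 50% | 10.9 | 14.6 | 0.25 | 1.3 | 2.5 | 5.0 |

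The range is about 1.3 (5 × 0.25 = 1.25) to 14 points (20 × 0.70). Even at the largest share, exceeding 10 points needs a gap above 10/0.70 = 14.3. This is a snapshot at course 3: lower-dose non-responders who respond in courses 3 to 6 would shrink s.

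**Step 4. The 2-in-both reading.** No non-responders remain in either arm, so s = 0 and this component is zero if response rates are equal. The other selection in Step 2 remains, and the documents give nothing from which to size it.

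**Step 5. The post-cycle-1 survey.** It comes before the response-based removal point on either reading. What still selects patients is early death (10 of 37, 27%, in the historical control), other early exits and non-return.

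**The case against.** The best defense has four parts.

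1. **The 2-versus-6 premise is not settled.** Sections 6.5.3 and 6.6 point to 2 courses without distinguishing arms, and then the unequal-removal component vanishes if response rates are equal. This stands, and is why the point cannot rest on that mechanism alone.

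2. **The endpoint is exploratory, descriptive and unpowered, and no post-course-2 contrast is named.** This limits the importance. It does not remove the problem: lack of power concerns precision, whereas this concerns which patients are observed, and Section 14.3.2 does announce a between-arm estimate.

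3. **Direction and size are not known.** A reader might infer that later QOL comparisons must favor the higher-dose arm whatever the true effect. The documents do not support that. They report no QOL by response status, lower-dose non-responders may continue but need not, and exits to transplant, other therapy or toxicity could offset the selection or add to it.

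4. **The affected period cannot be put in months.** A reader might multiply courses by 28 to 35 days. In Section 6.5 that is the marrow window after the first course, not a cycle length. Later courses wait on toxicity recovery, and Section 6.6 allows up to 6 weeks from CR/CRi.

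Nor may the post-cycle-1 survey be assumed to fall at the marrow visit. Section 8.2.1 ties it to no visit, and the marrow is taken at count recovery or Days 28 to 35, whichever is first, so its timing may differ by arm.

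**Conclusion.** The point holds as a minor one. With surveys requested only on study, between-arm QOL differences after course 2 can partly reflect who is still surveyed, and the plan has no provision for this. That conclusion survives either reading of the induction limit; the mechanism and size do not. On the 2-versus-6 reading, an artifact of about 1.3 to 14 points is possible with no true effect, against an important difference of 10, but only under the assumed response rates, continuation rates and QOL gaps. On the 2-in-both reading that component is zero if response rates are equal, and selection by response, transplant and the 4-versus-12 caps is left unquantified. It would be too strong to say that later differences simply are selection, or that they necessarily favor the higher-dose arm.

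**What to change.** 1. Reconcile Sections 6.0 and 10.1.4 with Sections 6.5.3 and 6.6 on the number of induction courses in each arm. Which rule is intended is for the investigators to decide.
2. State in Section 14.3.2 that the between-arm QOL contrast is the post-cycle-1 survey, collected in one window counted from day 1 and the same for both arms, and adjusted for the enrollment score. Report by arm the deaths and non-returned surveys before it.
3. Present randomized patients separately from those who chose their arm. Section 14.1 allows both routes, and Section 14.3.2 groups patients by treatment received; adjusting for enrollment QOL alone does not make self-selected groups comparable.
4. Show later surveys by time since day 1 and treatment status, as within-arm description conditional on remaining on treatment.

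**Cost.** A short analysis statement and a survey window; no additional surveys. The plan gives up any between-arm QOL claim beyond cycle 1. The randomized contrast will also be small: at the feasibility threshold of 26 randomized patients it has about 13 per arm, or 13 × 0.73 ≈ 9.5 alive to be surveyed if the 27% historical early-death rate applied to both arms. It should be reported as an estimate with its interval, in keeping with the stated exploratory aim.

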8.2.2 Evaluation of medical complications and use of medical resources

Information on medical complications (e.g. need for intensive care unit (ICU)-level care, length of ICU stay, neutropenic fever, documented infections, bleeding, reasons for hospitalization, etc.) and use of medical resources (e.g. red blood cells and platelet transfusions; days of IV antimicrobial therapy, total hospital length of stay) will be collected from the medical records from the UWMC and SCCA as done previously.^{21,22}

8.2.3 Assessment of cost

The costs associated with inpatient and outpatient management will be calculated using electronic billing information from the UWMC and SCCA. Costs will be converted from charges using departmental cost-to-charge ratios. We anticipate reporting descriptive information identifying major cost drivers and total/subset costs per phase of treatment (i.e. induction, outpatient management, and readmission), similar to our approach used previously.^{21,22}

8.2.4 Examination of patient and physician attitudes towards medical decision-making and treatment allocation

8.2.4.1 We will explore patient-reported factors influencing medical decision-making through a Patient Preference Survey (APPENDIX D) distributed on study enrollment. This survey will include a question on whether they agree to be randomized or prefer to choose their treatment arm, and explores the reasons underlying this decision. As above, given that patients do not always fill out questionnaires, we will measure percentage of returned responses regarding reasons for treatment decision-making as one of our feasibility outcomes. Surveys not returned will not be considered a protocol deviation.

8.2.4.1 We will also explore physician preferences towards treatment-intensity randomization through a Physician Preference Survey (APPENDIX E) also distributed on study enrollment. This survey includes questions about whether the physician was agreeable to randomization (even if the patient was not) and explores reasons the physician might have not wanted to randomize the patient. As physicians are extremely busy, we will measure percentage of returned responses regarding reasons for treatment decision-making as one of our feasibility outcomes. Surveys not returned will not be considered a protocol deviation.

